## 6 STUDY INTERVENTION(S) OR EXPERIMENTAL MANIPULATION(S)

### 6.1 STUDY INTERVENTION(S) OR EXPERIMENTAL MANIPULATION(S) ADMINISTRATION

#### 6.1.1 STUDY INTERVENTION OR EXPERIMENTAL MANIPULATION DESCRIPTION

Teen-led workshops cover behavioral skills including goal setting, self-monitoring, problem solving, contingency management, coping skills, and social support. Workshop topics include explanation of pre-diabetes/diabetes, label reading, healthy plate planning, portion control, finding affordable healthy foods, strategies to increase physical activity, and coping with eating triggers and social pressures. Participants create and report on action plans with weekly goals, brainstorm to solve problems, and communicate between sessions. The intervention is 12 weekly 90-minute workshops based on feedback from our community advisory board and experts in peer led health education programs. The intervention will be offered via an online platform, Zoom, which is HIPAA compliant. We are testing the effectiveness of the virtual program.

For participants in the text message pilot program we will obtain parental permission to allow mPulse Mobile to receive their cell phone numbers and send SMS text messages to participants. This information will be included in the study consent form with a separate place within the consent form for parents to initial to give this permission. Participants aged 18-19 will be asked to sign their own permission to receive SMS text messages from mPulse Mobile. We will make it very clear to participants that what is shared through the mobile dialogue is private, secure, and not shared with anyone beyond the program. We will also express that standard data and messaging rates from participant's provider may apply and that they can request that messages stop being sent at any time. Participants in the waitlist control will also be asked to consent to giving their phone numbers to mPulse

#### 6.1.2 ADMINISTRATION AND/OR DOSING

Full-Dose: Attendance to all 12 workshops

Half-dose: Attendance to 6-11 workshops

Participants attending less than 4 workshops will be considered as "not adhering to the project"; however, they will not be removed from the study.

### 6.2 FIDELITY

#### 6.2.1 INTERVENTIONIST TRAINING AND TRACKING

The principal investigator and clinical research coordinator will be responsible for screening potential peer leaders to ensure that they are appropriate for being in a leadership position with younger teens. Potential peer leaders will likely be referred by staff at our collaborating youth organizations who have been working with these youth for years. Interested youth will complete applications. We will conduct thorough interviews and also contact adult references provided as part of the leader selection process. Youth peer leaders will receive training about the workshops and communication/leadership skills and will be supervised by experienced adults throughout the study.

All members of the study team will be adequately trained on the protocol through planning meetings prior to the launch of this study. New study members will be trained through the use of scripts and a training manual developed for all trial-related functions. This training manual includes detailed instructions for each recruitment event, including participant checklists, device protocols, and results explanations. Research staff will use the scripts provided in the training manual for all study events. Debriefing will occur after each recruitment and follow-up event to confirm procedures and adherence to protocol.

#### 6.3 MEASURES TO MINIMIZE BIAS: RANDOMIZATION AND BLINDING

We are not randomizing participants for this pilot study.

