**Study Description:**

Specific Aims: 1) Explore strategies for using peer educators and novel mobile health technologies as part of a group lifestyle change program for diabetes prevention among at-risk ethnic minority youth in a New York City community with high disease burden. 2) Refine, implement, and evaluate outcomes for the intervention. Using preliminary data, we will use CBPR to refine our developmentally and culturally appropriate lifestyle intervention for pre-diabetic ethnic minority adolescents. We will then screen at-risk adolescents for pre-diabetes and related lifestyle and biological measures and compare outcomes in adolescents in intervention and wait list control groups to test intervention effectiveness. 3) Further refine the intervention for a larger RCT based on an examination of intervention feasibility, acceptability, and sustainability.

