We then recruited participants ages 13-19 who are at risk for diabetes through community youth organizations, health centers and schools, determined eligibility (overweight/obese by measured BMI), and invited them to return fasting for further evaluation. Those ages 13-17 required assent/parental consent, while those  $\geq 18$  signed their own consent. We screened teens for pre-diabetes using an oral glucose tolerance test (OGTT), obtained body measurements, blood pressure and metabolic tests, and administered a health and lifestyle survey. We screened 148 teens, of whom 90 were diagnosed with pre-diabetes (61%) and were randomized to intervention (n=41) and wait list control (n=49) groups. Each workshop group (10-15 teens) met for 90 minutes weekly for 12 weeks. All activities were delivered under the supervision of experienced adult health educators by youth peer leaders who underwent training including team building, group facilitation, and review of the workshop curriculum. We collected 5 and 12

month follow up data (73% retention at both time points). Information from this previous cohort will be used to refine our study.

In order to maximize the reach of this intervention, and with increasing need due to the pandemic, we are proposing a virtual component to the TEEN HEED program.

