### 2.3.2 KNOWN POTENTIAL BENEFITS

### 2.3.3 ASSESSMENT OF POTENTIAL RISKS AND BENEFITS

## 3 OBJECTIVES AND ENDPOINTS

OBJECTIVES	ENDPOINTS
Primary	
Use an iterative process between academic and community partners to adapt and modify the pilot TEEN HEED intervention	1) maintain/reduce body mass index (BMI)
Use qualitative methods to evaluate strategies for using peer educators and novel mobile health technologies as part of a group lifestyle change program for diabetes prevention among at-risk ethnic minority youth	2) improve adolescent dietary, physical activity and weight control behaviors, and
Use community-based participatory research strategies to refine, test, and evaluate outcomes of a peer education diabetes prevention program for pre-diabetic ethnic minority adolescents.	3) improve other measures of diabetes risk. We are collecting data at baseline and post intervention. We are also obtaining additional qualitative data and examining feasibility and acceptability for a text messaging program to support teens as they make lifestyle changes.

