## 4 STUDY DESIGN

### 4.1 OVERALL DESIGN

We are now testing and evaluating outcomes of our refined intervention to reduce diabetes risk among ethnic minority pre-diabetic adolescents. We will further adapt the program for virtual delivery via a video conferencing platform to enhance access and attendance, and refine the text messaging platform to better support and engage teens.

We will identify at risk for diabetes adolescents and recruit adolescents (BMI in the overweight/obese range and HbA1c 5.7-6.4%) through electronic medical record data queries and referrals from clinical and community sites. Participation will be contingent on adolescent assent/parental consent (ages 13-17) or participant consent (ages 18 years or older). We will randomize pre-diabetic adolescents into intervention and wait list control (delayed intervention) groups to test intervention effectiveness. We will also evaluate the virtual and mHealth components of the intervention through usability testing and data analytics.

The intervention is 12 weekly 90-minute workshops based on feedback from our community advisory board and experts in peer led health education programs. The intervention will be offered via an online platform, Zoom, which is HIPAA compliant. We are testing the effectiveness of a virtual component versus our previous in-person workshop.

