#### 4.4 END-OF-STUDY DEFINITION

A participant is considered to have completed the study if he or she has completed the baseline assessment and the follow-up assessment or has completed the text messaging program.

The end of the study is defined as completion of the 3-month follow-up assessment shown in the Schedule of Activities (SoA), **Section 1.3**.

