We will obtain only the minimum amount of PHI necessary to contact potentially eligible teenagers. We will meet with providers and ask them to consent to contacting their patients who they think may be eligible. Contact information will be immediately deleted from the server for those who are not interested in participating or who are not eligible for the study. Participants will be given the opportunity to decline being re-contacted should they not be interested in participating.

For Collaborating Community sites – As described above, site leaders will verbally inform potential subjects about TEEN HEED and provide interested children with a letter for parents. For adolescents ages 18 or 19 years who meet eligibility requirements and are interested in the study, we will obtain informed consent prior to participation in the study. For adolescents ages 13-17 years, who meet eligibility requirements and are interested in the study, we will obtain assent of the adolescent and obtain consent from his/her parent or guardian. The combined Parental Consent and HIPAA Authorization Form will be obtained in person or over the phone by a member of the study staff. After consent is obtained, we will invite adolescents for their official baseline visit. Eligible adolescents will be randomized into intervention and wait list control groups. Intervention participants will attend a 12-week peer led workshop and follow up assessments.

We will recruit potential peer leaders through our contacts at community youth organizations in East and Central Harlem and local schools. Peer leaders will attend training sessions, workshop

sessions and debriefing sessions. All classes will be led by trained adolescent peer leaders. Qualifications to be a peer leader are: 1) older than 18 years of age 2) fluency in English and 3) ability to communicate well in a group setting. Peer leader training will include information about not divulging information (e.g., conditions, treatments, personal background or any other confidential or non-public information) concerning participants attending the classes. We will also have the leaders sign a Statement of Confidentiality. Peer leaders will be paid \$100 to attend the training session and \$300 for leading each 12 week workshop

Participants will be given a \$40 gift card at each study visit as compensation for their time.

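### Sections 4.1 and 5.5 randomise to a wait-list control, Section 6.3 says nobody is randomised, and the analysis text defines no between-group contrast for the comparison the synopsis promises

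*Combined protocol and SAP*

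**What the plan says.** **Text that describes a concurrent control group.** The synopsis (Section 1.1, Study Description) undertakes to "compare outcomes in adolescents in intervention and wait list control groups to test intervention effectiveness". Section 4.1 says "We will randomize pre-diabetic adolescents into intervention and wait list control (delayed intervention) groups to test intervention effectiveness", and Section 5.5 says "Eligible adolescents will be randomized into intervention and wait list control groups". Section 6.1.1 adds that wait-list participants will be asked to agree to share their phone numbers with the texting vendor.

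**Text that denies randomisation.** The whole of Section 6.3, the section meant to describe randomisation and blinding, is "We are not randomizing participants for this pilot study".

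**Analysis text.** Sections 9.1 and 9.4.1 test hypotheses by comparing baseline with follow-up. Section 9.4.1 states the primary hypothesis for intervention participants only. It lists t tests without saying whether they are paired or two-sample, a matched-pairs signed-rank test for ordinal endpoints, and regression and mixed models with the baseline value, time and potential confounders as covariates. It asks for confidence intervals around intervention parameters but does not say what those parameters are. Section 9.4.2, on the primary endpoint, is a heading without text.

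**Timing.** The Section 1.3 schedule has one track with a baseline and a 3-month visit. Section 3 says "We are collecting data at baseline and post intervention", and Section 4.4 says "The end of the study is defined as completion of the 3-month follow-up assessment". The synopsis, however, gives in-person visits at baseline, 5 and 12 months and a participant duration of 12 months.

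**The concern.** Sections 4.1 and 5.5 cannot both stand with Section 6.3 for the same participants. Staff cannot follow all three, and a reader of the results could not tell whether they are randomised, non-randomised controlled or single-arm evidence.

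The analysis text does not resolve this, because it never names the contrast that answers the effectiveness question. If the pre-post change is used for that purpose, three other explanations remain open:

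- secular change over the months of follow-up;
- growth, in so far as age and sex referencing does not remove it;
- regression to the mean, since participants are selected for high BMI and raised HbA1c. For BMI this is reduced where eligibility came from an earlier medical-record value and baseline is measured anew at Visit 1.

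A concurrent control group would share these influences. A single group has nothing to set against them.

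**Working it through.** **1. Is the randomisation text only history?** Section 2.2 reports the earlier cohort separately and in the past tense: 90 teens "were randomized to intervention (n=41) and wait list control (n=49) groups". Sections 4.1 and 5.5 use the future tense, and Section 4.1 sets randomisation beside the new virtual delivery. As written, it applies to the current study. It may have been carried over from the earlier protocol, but nothing says so.

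**2. Is Section 6.3 limited to the texting pilot?** Section 4.1 says texting will be piloted in people enrolled in an earlier version of the study, so the word pilot in Section 6.3 could refer to that. Section 6.3 states no such limit. If it were so limited, no allocation method would be given anywhere for the workshop comparison.

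**3. Which design do the other sections fit?**

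| Fits a single-arm 3-month pilot | Fits a wait-list design |
|---|---|
| 1.3: one-track schedule | 1.1 Study Description: comparison of groups |
| 3: data at baseline and post intervention | 4.1 and 5.5: randomisation |
| 4.4: end of study at 3 months | 6.1.1: wait-list participants |
| 6.3: no randomisation | 1.1: visits at 5 and 12 months, 12-month duration (the earlier randomised cohort's follow-up times, Section 2.2) |

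The schema in Section 1.2, which might show the arms, is not visible in the text available. The documents do not settle the question.

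**4. Is there a between-group contrast?** Section 9.4.1 names the baseline value, time and confounders as model terms. It names no arm term and no arm-by-time term. The intervention parameter it mentions could belong to a two-group model but is not defined.

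**5. What could an uncontrolled test show?** The plan gives no sample size, alpha, SD or drift for this study (Section 9.2 is empty), so there is no figure to reproduce. Everything in this step is an assumption.

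- n: the earlier cohort's 41 intervention participants × 0.73 overall retention = 29.9, taken as 30. That retention was at 5 and 12 months, not 3.
- Test: paired t, two-sided 5%, 29 degrees of freedom, critical value 2.045.
- True intervention effect: zero.
- Drift d: in units of the SD of change, in the favourable direction.

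The probability of a significant reduction is P(T > 2.045), where T is non-central t with 29 degrees of freedom and non-centrality d√30.

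| d | d√30 | P(significant reduction) |
|---|---|---|
| 0 | 0 | 2.5% |
| 0.1 | 0.548 | 7.6% |
| 0.2 | 1.095 | 18.4% |
| 0.3 | 1.643 | 35.5% |

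At d = 0.2 the figure is 13% with n = 20 and 23% with n = 40.

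**6. Precision of a between-group contrast.** Controls: 49 × 0.73 = 35.8, taken as 36. With equal SDs of change and no baseline adjustment, the standard error relative to the pre-post one is √(1/30 + 1/36) / √(1/30) = 0.2472 / 0.1826 = 1.35.

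**The case against.** The best defence is that this is a single-arm pilot. Section 6.3 calls it a pilot and rules out randomisation, the schedule and end-of-study definition fit one group followed for 3 months, and the synopsis looks ahead to a larger randomised trial. On that reading the pre-post analysis is coherent, and the leftover wait-list and effectiveness wording is what is wrong. This stands as a possible resolution, and it is why the fix offers a single-arm route. It does not remove the problem: the synopsis and Sections 4.1, 5.5 and 6.1.1 would still describe a comparison that will not happen.

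The opposite defence is that Section 9.4.1 already allows a two-group model. It adjusts for confounders, lists time separately and asks for intervals around intervention parameters. That also stands as a possibility, but the contrast still has to be written down.

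A reader might therefore infer that the trial will certainly test effectiveness without a control, or that randomisation has been dropped. The documents support neither. They support only that an uncontrolled test may be what is done.

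It is also fair to object that no document supports any particular drift, or a favourable direction. The percentages show how the test behaves and do not predict this trial's result.

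**Conclusion.** The contradiction over allocation is real, and nothing in the documents resolves it. The comparison promised in the synopsis has no defined contrast in the analysis text. Whether the study is randomised, non-randomised controlled or single-arm cannot be determined, so neither can the strength of its main result. This must be fixed before analysis.

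That conclusion rests on the text alone. The size of the possible error rests on the assumed n and drift: a false finding of reduction rises from 2.5% to between 8% and 36% for favourable drifts of 0.1 to 0.3 SD of change at n = 30.

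**What to change.** State one design throughout, and reconcile Sections 1.1, 1.3, 4.1, 4.4, 5.5, 6.1.1 and 6.3, including the visit times.

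**If there is a wait list:**
- Make the primary test the between-group difference in the follow-up BMI measure, adjusted for its baseline value. Analyse participants as allocated and keep pre-post change descriptive.
- Use the mixed models already listed in Section 9.4.1 to account for workshop group in the intervention arm. The earlier cohort was taught in groups: "Each workshop group (10-15 teens) met for 90 minutes weekly for 12 weeks".
- Show the control group's visits in the schedule.
- If allocation is randomised, correct Section 6.3 and state the method. If it is not, also adjust for the listed confounders and label the evidence non-randomised.

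**If the study is single-arm:**
- Delete the randomisation and wait-list wording in Sections 1.1 (Study Description), 4.1, 5.5 and 6.1.1.
- Change the effectiveness wording in Sections 1.1 (Study Description and Endpoints), 4.1, 6.1.1, 8.1, 9.1 and 9.4.7 to pre-post change.
- Report mean change with a 95% confidence interval as pilot data.

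**In either case,** Section 4.1 also claims a test against the earlier in-person workshop, for which no analysis is given. Delete that claim or label it a descriptive historical comparison.

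**Cost.** The single-arm route needs wording changes only but narrows the claim. The between-group contrast is less precise: its standard error is about 1.35 times the pre-post one at an assumed 30 versus 36, before baseline adjustment. Few workshop groups also leave few degrees of freedom.

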#### 6.4 STUDY INTERVENTION/EXPERIMENTAL MANIPULATION ADHERENCE

#### 6.5 CONCOMITANT THERAPY

N/A

#### 6.5.1 RESCUE THERAPY

N/A

### 7 STUDY INTERVENTION/EXPERIMENTAL MANIPULATION DISCONTINUATION AND PARTICIPANT DISCONTINUATION/WITHDRAWAL

#### 7.1 DISCONTINUATION OF STUDY INTERVENTION/EXPERIMENTAL MANIPULATION

When a subject discontinues from the study intervention (12-week workshop) but not from the study, remaining study procedures will be completed as indicated by the study protocol. If a clinically significant finding is identified (including, but not limited to changes from baseline) after enrollment, the investigator or qualified designee will determine if any change in participant management is needed.

The data to be collected at the time of study intervention discontinuation will include the following:

- The reason(s) for discontinuing the participant from the intervention, and methods for determining the need to discontinue
- If the participant is due to complete assessments within 2 weeks of being discontinued from the study intervention, those assessments will be administered at the time of discontinuation; if the next scheduled assessments are more than 2 weeks from the discontinuation date, the discontinued participant will wait for the next scheduled assessment. Thereafter, the participant will be included in all future scheduled assessments, even though not participating in the intervention.

## 7.2 PARTICIPANT DISCONTINUATION/WITHDRAWAL FROM THE STUDY

Participants are free to withdraw from participation in the study at any time upon request.

An investigator may discontinue a participant from the study for the following reasons:

- Significant study intervention non-compliance, unless varying compliance is an aspect of the study objectives
- Lost-to-follow up; unable to contact subject (see **Section 7.3, Lost to Follow-Up**)
- Any event or medical condition or situation occurs such that continued collection of follow-up study data would not be in the best interest of the participant or might require an additional treatment that would confound the interpretation of the study
- The participant meets an exclusion criterion (either newly developed or not previously recognized) that precludes further study participation

Subjects who sign the informed consent form, and subsequently withdraw, or are discontinued from the study, will not be replaced.

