## 5.2 EXCLUSION CRITERIA

An individual who meets any of the following criteria will be excluded from participation in this study:

- <13 or >19 years of age
- Previous diagnosis of diabetes
- BMI percentile <85th percentile for age and gender based on Centers for Disease Control and Prevention definition
- Hemoglobin A1c outside of the prediabetes range (<5.7% or >6.4%)
- Currently pregnant
- Speaking a language other than English (resources to translate and implement all study activities in other languages are limited at this time)
- Cognitive or physical impairment that would preclude comprehension of a conversation and communicating as part of a group (i.e., dementia, deafness, inability to speak)
- On medications that may raise or lower blood sugar
- Plans to relocate from New York City within one year of enrollment
- Had, or is planning to have gastric bypass surgery
- Has a pacemaker or other implanted electronic device

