## 8.3.4 TIME PERIOD AND FREQUENCY FOR EVENT ASSESSMENT AND FOLLOW-UP

The occurrence of an adverse event (AE) or serious adverse event (SAE) may come to the attention of study personnel during study visits and interviews of a study participant presenting for medical care, or upon review by a study monitor.

All AEs, not otherwise precluded per the protocol, will be captured on the appropriate case report form (CRF). Information to be collected includes event description, time of onset, clinician’s assessment of severity, relationship to study procedures (assessed only by those with the training and authority to make a diagnosis), and time of resolution/stabilization of the event. All AEs occurring while on study will be documented appropriately regardless of relationship. All AEs will be followed to adequate resolution.

Any medical or psychiatric condition that is present at the time that the participant is screened will be considered as baseline and not reported as an AE. However, if the study participant’s condition deteriorates at any time during the study, it will be recorded as an AE.

Changes in the severity of an AE will be documented to allow an assessment of the duration of the event at each level of severity to be performed. Documentation of onset and duration of each episode will be maintained for AEs characterized as intermittent.

<Insert role or name> will record events with start dates occurring any time after informed consent is obtained until 7 (for non-serious AEs) or 30 days (for SAEs) after the last day of study participation. At each study visit, the investigator will inquire about the occurrence of AE/SAEs since the last visit. Events will be followed for outcome information until resolution or stabilization.

---

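### Section 7.2 allows study exit because an additional treatment might confound the results, so 3-month BMI can be lost in an outcome-related way, with no rule for what is still collected or analysed

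*Combined protocol and SAP*

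**What the plan says.** Section 7.2 opens its list with "An investigator may discontinue a participant from the study for the following reasons". Two of the four reasons matter here.

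- The third reason has two limbs. One concerns the participant's best interest. The other applies when an event, condition or situation "or might require an additional treatment that would confound the interpretation of the study".
- The fourth reason is "The participant meets an exclusion criterion (either newly developed or not previously recognized) that precludes further study participation". Section 5.2 lists among the exclusions "On medications that may raise or lower blood sugar".

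Section 7.2 adds that discontinued participants are not replaced. It does not say what is measured after such an exit.

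Section 7.1 deals with a different group: "When a subject discontinues from the study intervention (12-week workshop) but not from the study, remaining study procedures will be completed". For them, "Thereafter, the participant will be included in all future scheduled assessments, even though not participating in the intervention". In the same spirit, Section 6.1.2 keeps participants with low workshop attendance in the study.

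Section 8.3.4 records events "until 7 (for non-serious AEs) or 30 days (for SAEs) after the last day of study participation". It also states "All AEs will be followed to adequate resolution".

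Sections 1.3 and 4.4 put the follow-up assessment at 3 months. The synopsis names visits at 5 and 12 months instead. Section 9.4.1 tests change from baseline to follow-up. Sections 9.3 and 9.4.2 have headings but no text.

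**The concern.** The second limb of the third reason protects the interpretability of the result, not the participant. It ends study participation, not only the workshop, and it is triggered by a possible need for treatment together with a judgement about confounding.

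Participants have overweight or obesity and an HbA1c in the prediabetes range, and a pediatric endocrine clinic is among the possible recruitment sites (Section 5.5). Outside treatment for worsening weight or glucose is therefore foreseeable. A participant whose own doctor starts such treatment could be taken out before the 3-month visit, so the BMI change would be computed without some of those with the poorest course. The primary hypothesis is that BMI does not rise, so missing data of this kind would favour it. The protocol would be creating the missing data itself, by a stated rule, when the measurement could still have been taken.

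**Working it through.** The plan gives no figure to reproduce. Section 9.2 has no text, so there is no sample size, SD or expected dropout. The check is a reading of the sections together, followed by an illustration with assumed inputs.

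**Step 1: is the endpoint lost?** In Section 1.3, height and weight are taken at baseline and at 3 months only. A participant removed in between has no follow-up BMI. If the synopsis visits at 5 and 12 months apply instead, removal before the first of them has the same effect.

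**Step 2: can the planned analysis recover it?** The paired comparisons in Section 9.4.1 need both values. Its models use the baseline value as a covariate, so with one post-baseline visit a participant without that visit contributes no outcome. Naming mixed models does not change this. No analysis population or missing-data rule is given.

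**Step 3: do Sections 7.1 and 8.3.4 close the gap?** Section 7.1 covers people who leave the workshop and stay in the study; Section 7.2 covers people who leave the study. Section 8.3.4 runs its window from the last day of participation, so it already allows for early exit. Neither restores the 3-month height and weight.

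**Step 4: how large could the shift be?** Assumptions:
- BMI change is normal and is expressed in SD units.
- A fraction q is removed, those highest on a normally distributed removal score.
- The score has correlation rho with BMI change.
- Neither q nor rho is in the documents.

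Shift in observed mean = −rho × φ(z) / (1 − q), where z is the (1 − q) quantile of the standard normal and φ its density.

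- q = 5%: φ(z) / (1 − q) = 0.1031 / 0.95 = 0.109
- q = 10%: 0.1755 / 0.90 = 0.195

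| q | rho = 0.3 | rho = 0.5 | rho = 1 (ceiling) |
|---|---|---|---|
| 5% | −0.03 SD | −0.05 SD | −0.109 SD |
| 10% | −0.06 SD | −0.10 SD | −0.195 SD |

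A check without the normal model: if the 10% removed average 1 SD worse than the overall mean, the rest shift by −0.10 × 1 / 0.90 = −0.11 SD.

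**Step 5: one arm or two?** In a single-arm before-after comparison, which Section 6.3 implies, the whole shift enters the result. Sections 4.1 and 5.5 describe randomization to a wait-list control. In that case the bias is the difference between the arms' shifts. With equal q, rho and SD it cancels. With q = 10% in one arm, 5% in the other and rho = 0.5, it is 0.0975 − 0.0543 = 0.043 SD. It favours the intervention if that arm loses more, and goes against it if the control arm does.

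**The case against.** A reader might infer that Section 7.2 contradicts Section 7.1. It does not. Section 7.1 limits itself to participants who remain in the study, and its sentence on clinically significant findings concerns participant management and is silent on assessments. Section 7.2 bypasses the retention principle of Section 7.1 without breaching its words.

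A reader might also infer that safety follow-up stops on removal. That is too strong. Section 7.2 is permissive. The investigator must already know of the triggering event in order to act on it, and Section 8.3.4 continues capture for 7 or 30 days and follows events until they resolve or stabilize. What can be lost is the inquiry at the later visit and new events after those windows.

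The direction of bias is not guaranteed. The third reason covers any event or situation, including illness unrelated to BMI or illness that lowers weight, and an added treatment might itself lower BMI.

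The investigator also has no scheduled BMI, questionnaire or glucose result between baseline and 3 months by which to pick out the worst changers. A correlation near 1 is therefore implausible, and the ceiling figures should not be read as estimates.

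Finally, the missing analysis rule is part of a wider gap in Section 9 that affects every dropout. All of this narrows the point. What remains is that a stated rule can remove an obtainable endpoint for reasons plausibly linked to outcome.

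**Conclusion.** The point holds in limited form. Section 7.2 permits discretionary, potentially outcome-related loss of the follow-up BMI through two bullets, and nothing in Sections 7.1, 8.3.4 or 9 says what is then collected or how these participants are analysed. If removal is linked to worsening, a single-arm result moves toward the study hypothesis. With 5% to 10% removed, the illustrative shift is about 0.03 to 0.10 SD at correlations of 0.3 to 0.5. The ceiling of 0.109 to 0.195 SD would need removal to track BMI change perfectly. Both the removal rate and the correlation are assumptions, and the true size cannot be derived from the documents. In a two-arm comparison only differential removal matters. The safety consequence is secondary. The change is worth making because it is cheap and the loss is avoidable.

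**What to change.** In Section 7.2, remove confounding of interpretation as a reason to end data collection. State that participants who receive additional treatment, or who newly meet an exclusion criterion after enrollment, still have the scheduled follow-up height and weight, questionnaire and adverse event inquiry, unless they withdraw consent or continued data collection is not in their best interest. Both bullets need this. If only the confounding wording is deleted, a participant started on a glucose-affecting medication can still be removed under the fourth reason.

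Record the additional treatment and its start date. Section 10.1.9.1 already lists concomitant medications among the data entered in REDCap, so little is added. In Section 9, state that these participants stay in the primary analysis, and add a sensitivity analysis that sets aside BMI measured after such treatment. Comparing the two shows how much the result depends on these participants.

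Reconcile Section 7.2 with Sections 7.1 and 8.3.4 on what is collected after discontinuation. This is a data-collection rule only; no rule on treatment or on stopping the workshop is proposed.

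Cost: two amended bullets, one start-date field and one extra analysis. The downside is that a few BMI values will include the effect of outside treatment, which the sensitivity analysis makes visible.
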